#### B. Primary feasibility outcome – visual screening

We will obtain serial taurine levels during ICU stay and Goldmann perimetry testing in the subjects are able to cooperate at 6 months follow up. Our goal is to achieve 90% completion rate for taurine levels, and have reliable visual field perimetry in ≥ 80% of survivors that regain consciousness following index hospitalization.

#### C. Primary pharmacologic outcome: PK – absorption

By analyzing serial VGB levels including baseline, we will validate the drug assay and characterize drug absorption; the target will be achieving a detectable VGB level in the serum of ≥ 80% of

enrolled subjects by 3 hours post-load. We anticipate detectable levels in all subjects by 12 hours. We expect peak concentrations to be delayed by one to three hours in older individuals receiving continuous enteral tube feedings.

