### Specific aims and hypotheses

**Prove the feasibility of enteral administration of a VGB load within 48 hours of PASE onset in resuscitated CA subjects.** We hypothesize that administering a single load of VGB within 48 hours of PASE onset is feasible. Later study phases will assess the potential therapeutic effects of this intervention.

**Demonstrate the pharmacokinetics (PK) of VGB absorption in the post-CA period.** We will follow VGB levels serially in the post-CA setting, in which there may be delayed absorption and impaired clearance. Delayed absorption is anticipated due to continuous enteral feeding, prevalent delayed gastric emptying, enteric mobility, and decreased enteric blood flow in the setting of neuromuscular blockade and vasopressors. Impaired clearance may occur due to a high prevalence of renal insufficiency and older age. We hypothesize that VGB will be detectable in ≥80% and 100% of subjects by 3- and 12h, respectively. We expect that peak concentrations will be delayed from 1 to 3h post-VGB in older individuals (≥65-year-old) receiving continuous enteral feeding, and that delayed clearance (detectable VGB after 72h) will occur in CrCl ≤30cc/min[62-64].

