### Primary outcome

#### A. Primary feasibility outcome – enrollment and drug delivery

We will primarily be looking at the ability to deliver VGB in PASE subjects; the target will be administering 4,500mg (or dose adjusted in moderate and severe impairment) of VGB enterally within **48 hours of PASE onset** in ≥ 80% of enrolled subjects. Given the lack of well-established alternative treatments in this deadly disease, we anticipate 60-75% enrollment of eligible subjects, and will therefore be tracking the ratio between eligible and enrolled subjects, consent rates, and reasons for decline in study participation.

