## 6. Trial design

Phase IIa: This is a feasibility, single center, open-label pilot, with blinded outcome assessment, of early administration a single 4,500mg (or dose adjusted in moderate and severe impairment) VGB in 12 consecutive PASE subjects.

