## Intervention period

### Drug administration

University of Florida (**UF**) Health Shands Hospital is enrolled in the Vigabatrin Risk Evaluation and Mitigation Strategy (**REMS**) program. The Vigabatrin drug supply for this protocol will be purchased, stored, and dispensed through the Investigational Drug Services Pharmacy satellite of the UF Health Shands Hospital Pharmacy Department. The study drug will be segregated from commercial supply Vigabatrin. Investigational supply would be dispensed upon enrollment, consent, and receipt of a valid order for investigational supply Vigabatrin by a protocol authorized prescriber. Prior to dispensing, the protocol-trained, REMS-trained pharmacist would verify the authorized prescriber, patient REMS enrollment, document the REMS ID numbers and obtain authorization to dispense through the REMS program.

Subjects will receive a **one-time loading dose of 4,500 mg of VGB** (or dose adjusted in moderate and severe impairment) in powder for oral solution formulation (9 packets of 500mg each, each mixed with 10 ml of water at room temperature, for a total of 90 ml of water and 4,500mg VGB dosing) will be administered via enteric tube (naso/orogastric or post-pyloric) within **48 hours of status epilepticus onset**. For subjects requiring a dose adjustment for renal impairment, the total volume administered will be dictated by dose of Vigabatrin (10mL of water for each 500mg packet).. If subjects are receiving the study drug through an NG/OG tube that is ordered to be connected to suction, the tube will remain clamped for a minimum of 30 minutes. Vigabatrin will not be co-administered with other enteral drugs, and no drugs will be given +/- 15 minutes of Vigabatrin administration (when possible per standard of care). Subjects will be considered screen failure if VGB is not administered within exact 48 hours from electrographic status epilepticus onset. This dose is in conjunction with a loading dose of ASD according to local practices and standard of care. This will be done within 48h of PASE onset in successfully resuscitated CA subjects.

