## 12. Statistical plan and data analyses

### Phase IIa sample size

12 subjects from the University of Florida

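### Delivery (primary outcome A) and absorption (primary outcome C) share the enrolled-subject denominator, which cannot serve both under the 48-hour screen-failure rule

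*Combined protocol and SAP*

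**What the plan says.** All references are to the combined protocol and SAP.

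- **Outcome A (section 4, enrollment and drug delivery).** The target is enteral delivery within 48 hours of PASE onset "in ≥ 80% of enrolled subjects".
- **Outcome C (section 4, PK – absorption).** The wording is "the target will be achieving a detectable VGB level in the serum of ≥ 80% of" followed by "enrolled subjects by 3 hours post-load. We anticipate detectable levels in all subjects by 12 hours".
- **Specific aims and hypotheses.** The same hypothesis appears with a looser base: "We hypothesize that VGB will be detectable in ≥80% and 100% of subjects by 3- and 12h, respectively".
- **Drug administration (section 6).** Drug release comes after enrollment: "Investigational supply would be dispensed upon enrollment, consent, and receipt of a valid order". The same section then states: "Subjects will be considered screen failure if VGB is not administered within exact 48 hours from electrographic status epilepticus onset".
- **Number of subjects.** Section 12 gives "12 subjects from the University of Florida" and section 6 refers to "VGB in 12 consecutive PASE subjects". Neither says whether the 12 are enrolled or dosed.
- **Analysis (section 12).** Feasibility outcomes are summarised with rates and proportions. No PK-evaluable set is defined, and the missing-data entry promises only that missing data will be reported.

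**The concern.** A delivery target below 100% carries information only if some enrolled subjects can miss timely dosing. An absorption target timed from the load makes sense only for people who had a load. One base is used for both.

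Enrolled but undosed subjects are foreseeable. The note on the inclusion window has consent sought once interictal epileptiform activity is seen, before PASE has developed. Dispensing follows enrollment, and consent can be withdrawn at any time.

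Outcome C is meant to show whether enteral vigabatrin is absorbed after cardiac arrest, and the rationale for the outcomes makes measurable levels part of the study's explicit purpose. With about 12 subjects, one or two who are never dosed can change the reading of C although absorption in those dosed was good. If the screen-failure rule removes them instead, A loses its meaning.

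**Working it through.** The plan derives no figure that could be reproduced: the sample size is stated without a calculation and power is omitted.

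**Inputs from the documents:** N = 12, taken here as 12 enrolled; threshold 80% for A and C.

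**Assumptions, not in the documents:** the number dosed, m; the probability a that a dosed subject has a detectable level by 3 h; the delivery probability d.

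**Step 1. Threshold.** 0.80 × 12 = 9.6, so 10 are needed. 10/12 = 83.3% meets the target; 9/12 = 75.0% misses it.

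**Step 2. Reading 1: a screen failure stays enrolled, and an undosed subject counts as not detectable.** C then needs 10 detectable whatever m is. On a dosed base it needs 0.80 × m, rounded up. With X ~ Bin(m, a), the chance of meeting C is P(X ≥ 10) on the enrolled base and P(X ≥ 0.80m rounded up) on the dosed base.

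| Dosed, m | A | Needed, enrolled base | Needed, dosed base | a = 0.80: enrolled / dosed | a = 0.90 | a = 0.95 |
|---|---|---|---|---|---|---|
| 12 | 100% | 10 of 12 | 10 of 12 | 0.56 / 0.56 | 0.89 / 0.89 | 0.98 / 0.98 |
| 11 | 91.7% | 10 of 11 | 9 of 11 | 0.32 / 0.62 | 0.70 / 0.91 | 0.90 / 0.98 |
| 10 | 83.3% | 10 of 10 | 8 of 10 | 0.11 / 0.68 | 0.35 / 0.93 | 0.60 / 0.99 |
| 9 | 75.0% | not attainable | 8 of 9 | 0 / 0.44 | 0 / 0.77 | 0 / 0.93 |

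For m = 10 and a = 0.90, the enrolled base gives 0.90^10 = 0.349. The dosed base gives P(X ≥ 8) = 0.930.

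A single data set shows the conflict. With 10 dosed and 9 detectable, A is met at 10/12 = 83.3%. C is 9/10 = 90% of those dosed (met) and 9/12 = 75% of those enrolled (missed).

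**Step 3. The same comparison with delivery random.** On the enrolled base X ~ Bin(12, d × a), and C is met if X ≥ 10. On the dosed base the chance is averaged over m ~ Bin(12, d).

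| a | Base | d = 0.80 | d = 0.90 | d = 1.00 |
|---|---|---|---|---|
| 0.90 | enrolled | 0.304 | 0.594 | 0.889 |
| 0.90 | dosed | 0.866 | 0.895 | 0.889 |
| 0.95 | enrolled | 0.422 | 0.753 | 0.980 |
| 0.95 | dosed | 0.965 | 0.979 | 0.980 |
| 1.00 | enrolled | 0.558 | 0.889 | 1.000 |
| 1.00 | dosed | 1.000 | 1.000 | 1.000 |

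On the enrolled base the result for C is driven largely by delivery; on the dosed base it hardly depends on it.

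**Step 4. Reading 2: a screen failure is no longer enrolled.** Everyone left was dosed within 48 hours, so non-delivery cannot lower C. For the same reason the timing part of A is m/m = 100% for any m, and the 80% target cannot be missed through lateness or non-delivery. A subject dosed after 48 hours, if there is one, would also leave the base for C, although that subject's levels bear directly on absorption.

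Under Reading 1, C is contaminated; under Reading 2, A is empty.

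**The case against.** The strongest reply is the screen-failure rule. If screen failures are not enrolled, and the 12 consecutive subjects are 12 dosed subjects, delivery cannot make C fail and the probabilities in Steps 2 and 3 do not apply. That reading is open on the text. It protects C only by emptying A, so the shared denominator still fails.

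A second reply is that the rationale states the purpose jointly, as delivery and then measurable levels, so an all-enrolled proportion is a coherent composite. It is, but the plan labels C as absorption and reports delivery separately as A.

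A third reply is that nothing formal turns on C. The analysis is descriptive, no go/no-go rule is attached, and a reader given both counts could recompute. This stands, and it limits the seriousness of the point.

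Three stronger readings are tempting, and the documents do not support them:

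- **That an unsampled subject counts as failed absorption.** No section says so. The missing-data entry leaves failure, exclusion and missing all open.
- **That one missed draw defeats the 3-hour target or the 12-hour expectation.** Both are worded as by the time point. The Drug absorption section schedules four post-dose draws up to 3 h (0.5, 1, 2 and 3 h) and six up to 12 h (adding 6 and 12 h), with venipuncture as back-up. The 12-hour figure is an expectation; the stated target is the one at 3 h.
- **That refusal of consent could make C fail.** A family that declines never enters the enrolled group, and outcome A tracks refusals separately. Only withdrawal after enrollment and before dosing could matter.

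**Conclusion.** The point holds as an inconsistency between two primary outcomes and the screen-failure rule. It does not show that the plan deliberately scores undosed subjects as absorption failures. Under either reading of enrolled, one of the two primary proportions does not measure what its label says.

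The thresholds are arithmetic on N = 12 and the 80% target: with 10 dosed, C needs 10 of 10 against 8 of 10, and with 9 dosed it is unattainable. These hold only if the 12 are enrolled subjects and undosed ones remain in the base. The contrast of 35% with 93% rests further on an assumed 90% detectability. With 10 dosed, over assumed detectability of 80% to 95%, the contrast runs from 11% against 68% to 60% against 99%; at 100% detectability it vanishes.

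The point should be corrected before data are read. Its weight is moderate, because the analysis is descriptive.

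**What to change.** 1. **Outcome C and the matching sentence in Specific aims and hypotheses.** Make the denominator all subjects who received any vigabatrin, whatever their 48-hour classification, and who are evaluable by the time point. Evaluable by 3 h (or 12 h) means either a detectable level at any post-dose draw up to that time, or a valid sample at 3 h (or 12 h) showing none. A subject with only an early undetectable draw is then not scored as a failure. Report the number dosed but not evaluable beside the proportion, since leaving such subjects out can flatter it.
2. **Outcome A and the Drug administration section.** Keep all consented and enrolled subjects with PASE as the denominator for A. Reconcile the screen-failure sentence with it by stating that a subject not dosed within 48 hours stays in that denominator as a delivery failure. This concerns classification in the analysis only and leaves the dosing window as it is.

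**Cost:** a few sentences in three places, with no new data collection. The PK denominator may fall below 12, with a correspondingly less precise proportion.

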### Secondary outcomes

- A. Secondary feasibility outcome – PASE detection and ultra-early drug delivery
  - a. We will track the proportion of subjects in whom PASE was present upon connection to EEG (onset misses) to explore alternatives to allow prompt EEG monitoring following ROSC.
  - b. We will also track the proportion of enrolled subjects who received a VGB load within 12 and 24 hours of PASE onset to explore the possibility of ultra-early administration of VGB in subsequent phases, as the internalization of GABAA receptors (a key mechanism of treatment refractoriness) is time-dependent[65].

- B. Secondary pharmacologic outcome: PK – elimination

By analyzing serial VGB levels, we will characterize drug elimination. We anticipate undetectable VGB levels in all subjects by 7 days regardless of their renal function. Subjects with normal renal function will have undetectable VGB levels by 72 hours, and those with creatinine clearance less than 30 mL/min will have detectable VGB levels at 72 hours.

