### Analysis methods

This feasibility pilot is not intended to detect therapeutic effects. Thus, we have omitted power calculations.

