### Primary outcome

Descriptive statistics with rates and proportions will be obtained regarding feasibility outcomes. Regarding the PK outcome, we will use the noncompartmental method for pharmacokinetic analyses. The key pharmacokinetic parameters, maximum concentration in plasma ( $C_{max}$ ) and the time to reach

maximum concentration ( $T_{max}$ ) will be determined directly from the plasma concentration-time profile of each participant. The area under the VGB concentration-time curve in plasma from zero to the time of the last quantifiable concentration ( $AUC_{0-t_{lqc}}$ ) will be calculated using the linear trapezoidal methods, and the AUC will be extrapolated to infinity for the evaluation of  $AUC_{0-\infty}$ .

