#### Secondary outcome

For exploratory aim 1, we will calculate the rate of retinopathy and the proportion of subjects with MRI changes. For exploratory aim 2, standard summary statistics will be provided for the post-VGB time to resolution of PASE, post-VGB time to start of anesthetic wean, overall number of anti-seizure drugs required for PASE resolution, total duration of anesthetic infusion for PASE treatment, duration of mechanical ventilation, intensive care unit length-of-stay, and cerebral performance category scale at hospital discharge and at 6 months.

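### Time from PASE onset to VGB load is to be summarised only as proportions at 12, 24 and 48 h; its median, spread and delivery curve are not planned

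*Combined protocol and SAP*

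**What the plan says.** Speed of delivery appears as an outcome in two places in Section 4.

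- **Primary outcome A** sets the target of giving the dose "of VGB enterally within 48 hours of PASE onset in ≥ 80% of enrolled subjects".
- **Secondary outcome A.b** reads: "We will also track the proportion of enrolled subjects who received a VGB load within 12 and 24 hours of PASE onset". It carries no target. Its purpose is "to explore the possibility of ultra-early administration of VGB in subsequent phases", and the reason given is that receptor internalization depends on time.

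On analysis, Section 12 (Primary outcome) states: "Descriptive statistics with rates and proportions will be obtained regarding feasibility outcomes". Section 12 (Secondary outcome) covers only exploratory aims; there, "standard summary statistics will be provided for the post-VGB time to resolution of PASE", along with other post-load intervals, durations and lengths of stay. The sample size is given as "12 subjects from the University of Florida", and on power the plan says "Thus, we have omitted power calculations".

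Two further rules bear on this time. Section 6 (Drug administration) classes a subject not dosed by 48 h from onset as a screen failure. Section 5 (Inclusion criteria) defines onset differently for the expanded group with presumed electroclinical status epilepticus: the clock starts at the antiseizure loading dose.

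**The concern.** The delay from PASE onset to load is a continuous time, and it is the quantity on which the feasibility aim turns. The plan gives summary statistics to intervals that start at the load but plans none for the interval that ends there. Planning a shorter window for a later phase needs the typical delay, how much it varies, and the share of subjects who would meet whichever window is being considered. Two or three counts out of 12 give this only coarsely: loads at 12.5 h and 23.5 h are scored alike, while loads at 11.5 h and 12.5 h fall on opposite sides. If nothing more is summarised, the pilot may report less about delivery speed than its own data could show.

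**Working it through.** **1. Where the time is summarised**

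| Place | Treatment of onset-to-load time |
|---|---|
| Section 4, Primary outcome A | Proportion within 48 h, target at least 80% |
| Section 4, Secondary outcome A.b | Proportions within 12 h and 24 h, no target |
| Section 4, Exploratory outcomes | Not listed; intervals start at the load or are durations |
| Section 8, Status epilepticus data | Not listed as an interval |
| Section 12, Primary outcome | Rates and proportions for feasibility outcomes |
| Section 12, Secondary outcome | Not listed; post-load times, durations and stays are |

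Section 4 (Rationale for chosen outcomes) also mentions tracking time for completion, but of the efficacy and safety measures.

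**2. What the proportions give at n = 12**

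The plan states no precision, so there is no figure of its own to reproduce. Exact (Clopper-Pearson) 95% intervals are:

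- 3/12 = 25%: 5.5% to 57.2%
- 6/12 = 50%: 21.1% to 78.9%
- 9/12 = 75%: 42.8% to 94.5%
- 10/12 = 83%: 51.6% to 97.9%

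The 80% target needs 0.8 × 12 = 9.6, so at least 10 of 12.

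**3. What the proportions leave open**

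The times below (hours) are invented for illustration.

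- Set A: 2, 3, 4, 13, 13, 13.5, 14, 14, 15, 30, 32, 35
- Set B: 10, 11, 12, 21, 22, 22.5, 23, 23, 24, 40, 44, 47

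| | Set A | Set B |
|---|---|---|
| Within 12 / 24 / 48 h | 3 / 9 / 12 | 3 / 9 / 12 |
| Median | (13.5 + 14)/2 = 13.75 h | (22.5 + 23)/2 = 22.75 h |
| Within 6 h | 3/12 | 0/12 |
| Within 18 h | 9/12 | 3/12 |
| Within 36 h | 12/12 | 9/12 |

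The planned report would be identical for both sets. It would place the median between 12 and 24 h and go no further.

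**4. What a continuous summary would add**

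A distribution-free interval for the median runs from the 3rd to the 10th ordered time. Its coverage is 1 − 2 × P(Bin(12, 0.5) ≤ 2) = 1 − 2 × (1 + 12 + 66)/4096 = 96.1%. In the illustration it is 4 to 30 h for set A and 12 to 40 h for set B, so it is wide, as any interval from 12 subjects will be.

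If enrolled subjects not dosed by 48 h are ranked last as beyond 48 h, the 10th ordered time is still observed with up to 2 such subjects, which is exactly when the 80% target is met. With 3 or more, the upper limit is reported as beyond 48 h. The median, the mean of the 6th and 7th times, is observed with up to 5.

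**5. Denominator**

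If screen failures under the 48 h rule leave the denominator, every remaining subject was dosed in time. The 48 h proportion is then 100% by construction, and only the 12 h and 24 h counts say anything about speed. Section 4 refers to enrolled subjects, and Section 6 does not say whether a consented subject who misses 48 h still counts as enrolled.

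**The case against.** The strongest reply is that this is silence, not a decision to dichotomise. The Section 12 sentence does not say that only proportions will be given, it sits under the primary outcome heading, and no analysis sentence addresses secondary outcome A.b at all. The exact times must be known to apply the 48 h rule, and Section 6 (Blinding) shows that the study holds the time of administration. A listing of 12 values is not ruled out. Moreover, a proportion is a natural answer to a question about a window, and undosed subjects count simply as failures. All of this stands. It means that the proportions should be kept and that the gap is an unplanned summary.

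A reader might infer that the delivery times are being discarded. The documents do not support that: the times have to exist, and they are merely not planned to be summarised.

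A reader might also infer a measurable loss of power or precision. As a benchmark, take 12 lognormal times with 80% below some cut, and test whether the median lies below that cut at one-sided 2.5%. A rule of 10 or more out of 12 has 56% power, against 76% for a t-test on log time. That contrast does not measure a loss in this trial:

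- No test is planned, and the hypothesis is not in the documents.
- The 80% is the 48 h target; 12 and 24 h have none.
- The binomial rule has actual size 1.9% against 2.5%, so the tests are not compared on equal terms.
- The t-test needs 12 observed times, but undosed subjects have none. At a true 80% within 48 h, all 12 are observed with probability 0.8^12 = 7%.
- The plan has three cuts. Under a normal model for log time with known spread, one cut at the 80th percentile keeps 49% of the information on location, while three well-placed cuts keep roughly 85-88%.

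Comparisons of estimation error under the same complete-data lognormal model fail for the same reason of missing times.

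**Conclusion.** The point holds as an omission of minor severity. Onset-to-load time is planned to be summarised only as proportions at 12, 24 and 48 h. With 12 subjects these cannot locate the typical delay beyond a bracket, show its spread, or give the share meeting a different window. That limits the stated purpose of exploring ultra-early administration.

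No conclusion, sample size or subject protection depends on it, and the proportions remain legitimate feasibility measures. The finding rests on the text of the outcome, data-list and analysis sections. The two sets of times show what is possible and are not a forecast. No power or efficiency figure is claimed as the size of the problem.

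**What to change.** Keep the 12, 24 and 48 h proportions and the 80% criterion. Then:

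1. In Section 4 (Secondary outcome A.b) and Section 12, name time from PASE onset to VGB load as a summarised variable: individual values, median with the interval from the 3rd to the 10th ordered time (96.1% coverage at n = 12), IQR and range.
2. Add a cumulative-delivery curve over 0-48 h, from which the three proportions can be read.
3. List the interval under Status epilepticus data in Section 8.
4. State that enrolled subjects not dosed by 48 h stay in the denominator as not delivered, and reconcile this with the screen-failure wording in Section 6.
5. Show the two onset definitions of Section 5 separately, by subgroup or by marking individual values, because a pooled summary would mix two time origins.

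The cost is a few sentences and one table or figure. It needs no new subjects, visits or measurements, since both times are already required to score the cuts.

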**Rationale for chosen VGB regimen:** A single VGB load is sufficient to achieve a prolonged GABA catabolism inhibition[55] and minimizes the risk of vision loss associated with chronic exposure. No toxicity has been reported with a single dose of VGB to date. The inhibition of central and peripheral GABA-t has been shown to outlast serum VGB elimination[55-57], demonstrating the irreversible nature of GABA catabolism inhibition[57, 58]. Vigabatrin has been tested up to 6,000mg daily doses in studies [59], including a study comparing placebo, 1,000/day, 3,000/day, and 6,000/day for a total of 12 weeks [60]. Additionally, 6,000/d dosing led to a similar therapeutic effect on seizure control than 3,000/d [60], but it was associated with increase sedation/drowsiness and led to higher proportion of patients discontinuing therapy. A dose ceiling effect has been set in initial studies of VGB, in which doses >60mg/kg failed to elevate cerebral GABA levels further[61], and prolonged elevations of cerebral GABA levels may reduce

GABA synthesis [61]. In an individual ~70 kg, 60mg/kg corresponds to 4,200mg. As absorption is expected to be lower in the post-cardiac arrest period (due to decreased gastrointestinal motility and gastric emptying), a single dose of 4,500mg was selected for patients with normal or mild renal impairment. Patients with moderate (CrCl 30-50mL/min) will receive 2,250mg (50% dose reduction), and patients with severe renal impairment (CrCl<30cc/min) will receive 1,125mg (75% dose reduction). Thus, to minimize toxicity risk, maximize synergistic potential with co-administration of GABA-ergic anesthetics and the therapeutic window, we selected a single loading dose of VGB.

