### Rationale for chosen outcomes

The phase IIa study is a feasibility study and is not powered to address efficacy or safety. We will collect these metrics and track percent of missing data and the time for completion to inform which clinical variables pertaining to efficacy and safety will become primary and secondary clinical outcomes in subsequent study phases.

The explicit purpose of this feasibility study is to deliver the drug within 48 hours of PASE onset and have measurable levels by 3-12 hours post-load in addition to completing visual screening. The reported bioavailability of VGB is 100%, with a wide volume of distribution, minimal binding to blood proteins and elimination mainly through renal clearance[42]. While plasma concentrations of VGB do not correlate with its effectiveness[42], they confirm successful absorption of this drug. Renal impairment is common after CA[66] and creatinine clearance influences VGB elimination[62]. Further, several other factors may affect VGB absorption in the post-CA period. Thus, we will follow serial VGB levels to characterize enteric absorption and clearance in this setting. Furthermore, given the potential for drug-drug interactions among ASDs, we will be monitoring other ASD levels. For example, up to a 20% reduction in total phenytoin plasma levels can be seen with co-administration of VGB[42, 67, 68], while up to a 10% increase in carbamazepine levels has been observed with co-administration of VGB[42].

Most landmark clinical trials with VGB did not include critically ill subjects. However, a recent trial evaluating the potential neuroprotective effects of VGB in severe traumatic brain injury demonstrated adequate absorption and elevated cerebral GABA levels as determined by microdialysis [53, 54]. Our study follows a design used in other studies, measuring serial VGB levels at baseline, 1, 3, and 12 hours following

VGB administration[53]; the addition of 0-, 0.5-, 1-, 2-, 3-, 6-, 12-, 24-, 48-, 72- and 168-hour (7 days) level measurements is aimed at accurately describing absorption, confirming clearance of the drug, and confirming the reported lack of correlation of drug levels with a sustained clinical effect. A pre-dose sample allows for confirmation that VGB is not already present in the study subjects and no interference in the quantification method.

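### An undetectable vigabatrin level at 72 h does not show normal clearance in subjects with CrCl <30 mL/min, because they receive a quarter of the full dose

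*Combined protocol and SAP*

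**What the plan says.** All references are to the combined protocol and SAP.

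- Section 4, Specific aims and hypotheses, predicts that "delayed clearance (detectable VGB after 72h) will occur in CrCl ≤30cc/min".
- Section 4, Secondary outcomes, item B, opens with a broad aim: "By analyzing serial VGB levels, we will characterize drug elimination". It then expects normal renal function to give undetectable levels by 72 h, while "those with creatinine clearance less than 30 mL/min will have detectable VGB levels at 72 hours". All subjects are expected to be undetectable by 7 days.
- Section 3, in the rationale for the vigabatrin (VGB) regimen, ties dose to renal function. The full dose is 4,500 mg; "Patients with moderate (CrCl 30-50mL/min) will receive 2,250mg (50% dose reduction") and "patients with severe renal impairment (CrCl<30cc/min) will receive 1,125mg (75% dose reduction").
- Section 12, Primary outcome, plans noncompartmental analysis with Cmax, Tmax and AUC to the last quantifiable level. The AUC "will be calculated using the linear trapezoidal methods, and the AUC will be extrapolated to infinity for the evaluation of" the area from zero to infinity. Clearance (CL/F), terminal half-life and dose normalization are not named.
- The Secondary outcome text in Section 12 does not mention elimination, and no assay limit is stated anywhere.

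**The concern.** The 72 h reading is meant to separate slow from normal elimination by renal group, but dose changes with the same renal grouping. Whether a level is detectable at a fixed time depends on the dose given, the volume, the half-life and the assay limit. A reduced dose therefore pushes the CrCl <30 group toward undetectable, the opposite of what the protocol predicts for it.

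At stake is the account of elimination that the plan promises. If CrCl <30 subjects turn out undetectable at 72 h, that could be reported as no delay in clearance when it reflects the smaller dose. Section 12 defers GFR subgroups to later phases, but Section 4 states this CrCl contrast for the present phase.

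**Working it through.** **Inputs from the documents.** Doses 4,500, 2,250 and 1,125 mg (Section 3); post-dose levels at 0.5, 1, 2, 3, 6, 12, 24, 48, 72 and 168 h (Section 6, Drug absorption); expected peak delay of 1 to 3 h in older tube-fed subjects (Section 4, primary outcome C).

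**The plan's own figures.** 4,500 × (1 − 0.50) = 2,250 and 4,500 × (1 − 0.75) = 1,125. Both reproduce.

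**Dose effect, free of assumed values.** 4,500/1,125 = 4 = 2². With equal half-life, bioavailability (F) and volume, and first-order elimination, the quarter dose reaches any fixed limit two half-lives earlier.

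**Size, under assumptions.** The documents give no volume, half-life or assay limit. Let R be the initial full-dose concentration divided by the assay limit. Ignoring the absorption phase, the shortest half-life still detectable at 72 h is 72/log2(R) for the full dose and 72/log2(R/4) for the quarter dose.

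| R | 4,500 mg | 1,125 mg | Ratio |
|---|---|---|---|
| 50 | 12.8 h | 19.8 h | 1.55 |
| 100 | 10.8 h | 15.5 h | 1.43 |
| 1,000 | 7.2 h | 9.0 h | 1.25 |
| 5,000 | 5.9 h | 7.0 h | 1.19 |

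Example at R = 100 and half-life 12 h: 72/12 = 6 half-lives. The full dose gives 100/64 = 1.56 times the limit (detectable) and the quarter dose 25/64 = 0.39 times (undetectable).

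**A missed delay.** Assume V = 60 L, F = 1, no absorption phase, and a limit of (4,500/60)/2⁸ = 0.293 mg/L. Suppose half-life is 5.5 h with normal function and 11 h at CrCl <30, so clearance is halved. The CrCl <30 subject has (1,125/60) × 2^(−72/11) = 18.75 × 0.0107 = 0.20 mg/L: undetectable, despite halved clearance.

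**Raw AUC.** AUC = F × dose/CL, so at equal F the ratio of quarter to full dose is (1/4) × the fold fall in clearance: 0.5, 1.0 and 2.0 for 2-, 4- and 8-fold lower clearance. At 4-fold the impairment is invisible.

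**CL/F on the planned samples.** One compartment, same V, F and limit, half-life 10 h, so true CL = 60 × ln 2/10 = 4.16 L/h. Absorption rate constant (ka) 1/h, linear trapezoid, slope from the last three quantifiable levels from 12 h, no assay error:

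- full dose: 0.548 mg/L at 72 h (detectable), CL/F 3.94 L/h;
- quarter dose: 0.137 mg/L (undetectable), CL/F 3.96 L/h.

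The reading flips with dose; CL/F does not.

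**Absorption.** With ka set so that the peak comes 3 h later (about 0.34/h), the quarter-dose level above rises only from 0.137 to 0.160 mg/L, still under 0.293. At ka 0.1/h it is 0.370 and detectable (CL/F 4.05 L/h), but the peak then moves from 2.9 to 11.9 h, a 9 h delay.

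**Cut-off wording.** Delayed clearance is predicted for CrCl ≤30 in the aims and for <30 in the secondary outcome; the regimen text puts 30–50 in the moderate band and <30 in the severe band. A subject at exactly 30 is moderate for dosing, inside the aims prediction and outside the secondary-outcome one.

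**The case against.** The strongest reply is that the planned contrast is not at equal half-life. The protocol expects renal function to affect elimination, and a large enough difference survives the dose reduction. With V = 60 L, ka 1/h and the 0.293 mg/L limit, the 72 h reading classes both groups as predicted for normal-function half-lives of 5.9–8.9 h if clearance is halved at CrCl <30, and 3.0–8.9 h if it is four-fold lower. That stands: the reading can work, and a detectable level after a quarter dose is stronger evidence of slow elimination. What remains is the undetectable reading, which cannot be interpreted.

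Second, the 72 h statements are expectations under a broader aim, and extrapolating AUC to infinity already needs a terminal slope. This also stands. CL/F and half-life can be derived, so no data are missing; but they are not named as measures, and the only stated meaning of delayed clearance is the detectability one.

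A reader might infer that absorption speed makes the reading unreliable in both directions. The documents do not support that. They anticipate delayed absorption ("Delayed absorption is anticipated due to continuous enteral feeding, prevalent delayed gastric emptying, enteric mobility, and decreased enteric blood flow") but quantify it as a 1 to 3 h later peak, which barely moves the reading. Another assumed case, a quarter dose with half-life 7 h and a 0.073 mg/L limit, also stays undetectable with a 3 h later peak (0.023 mg/L). Only much slower absorption, or a subject very near the limit, would change the class.

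**Conclusion.** The point holds for one direction of error. An undetectable 72 h level in a CrCl <30 subject does not show normal clearance, because dose and renal group are tied and the quarter dose costs two half-lives. That result needs only first-order elimination with equal half-life, F and volume. The 1.2- to 1.55-fold difference in threshold half-life and the concentration examples rest on assumed values, and the number of CrCl <30 subjects among the 12 is unknown, so the practical impact cannot be sized.

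It would go too far to say that elimination cannot be assessed in this study or that the late samples are of no use. The planned levels support CL/F, and Section 4 gives them the purpose that the schedule "is aimed at accurately describing absorption, confirming clearance of the drug"; the 7-day level can serve as a check that the dose actually given has gone. No test or go/no-go rule rests on the 72 h reading. Priority is low to moderate.

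**What to change.** Analysis and wording only; no dose change is proposed.

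1. Base the elimination outcome on per-subject CL/F = actual dose/AUC to infinity, with terminal half-life as support. Show individual values against CrCl and flag renal replacement therapy, which can change clearance during sampling.
2. Dose-normalize Cmax and AUC, or report them by dose stratum.
3. Keep 72 h and 7-day detectability as description by dose stratum, with the assay limit stated, and not as the definition of delayed clearance.
4. State how many levels each terminal slope uses, and flag subjects with fewer than three quantifiable levels from 12 h on.
5. Reconcile the CrCl cut-off wording across the regimen rationale, the aims and the secondary outcome.

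No added samples or assays are needed, but there are limits. CL/F also reflects F. Very slow absorption distorts half-life more than CL/F: in the assumed model at ka 0.1/h, for quarter-dose subjects in the affected range, half-life is overstated by 15–58% while CL/F is 1–8% low, so the two should be read together. Late levels can be few: in the quarter-dose example at ka 1/h, only those at 12, 24 and 48 h are quantifiable, so losing one would flag the subject.
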